7.4 Analysis

Continuous variables were reported as medians with interquartile ranges (IQRs), and categorical variables were reported as frequencies with percentages. The Kruskal-Wallis test was used to compare continuous variables, and the chi-squared test was used to compare categorical variables. Kaplan-Meier curves and the log-rank test were used to compare patient and graft survival rates. Cox-regression was performed to identify the risk factors for death-censored graft failure. Variables with a p-value < 0.1 in the univariate analysis were included in the multivariate analysis. The proportional hazards assumption was evaluated through Schoenfeld residuals. A two-sided p-value < 0.05 was considered statistically significant. All statistical analyses were conducted using R version 4.2.2.

8. Ethical considerations

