UAVG	Dutch Act on Implementation of the General Data Protection Regulation; in Dutch: Uitvoeringswet Algemene Verordening Gegevensbescherming
WMO	Medical Research Involving Human Subjects Act, in Dutch: Wet Medisch-wetenschappelijk Onderzoek met Mensen

**Please add any new definitions that are used in the research protocol*

Summary

Rationale

The impact of donor and recipient sex combinations on kidney transplant outcomes has been widely studied, yet results remain inconclusive. Immunologically, female recipients of male donor kidneys face higher graft failure and mortality risks due to H-Y antigens. Another theory suggests male recipients of smaller female kidneys have worse outcomes due to nephron overload and hyperfiltration. Estrogen's protective effect against ischemia-reperfusion injury (IRI) lowers delayed graft function (DGF) incidence in female recipients, but recent research indicates higher mortality and graft loss rates for female recipients compared to males. These conflicting findings mainly pertain to deceased donor transplants.

For living donor kidney transplants (LDKT), previous study reported that male recipients of male donor kidneys had better graft survival in a study of 30,258 LDKTs from 1990-1999. Another study of 5,716 HLA-identical sibling transplants from 1985-2000 showed female recipients had better graft survival regardless of donor sex. Despite clinical advances, no large-scale studies have explored this issue in the last two decades.

Objective(s)

1. To investigate the impact of different donor and recipient sex combinations on the graft survival following living donor kidney transplantation
2. To investigate the impact of different donor and recipient sex combinations on the graft function (eGFR) following living donor kidney transplantation

Study type

Retrospective cohort study

Study population

Adult patients (n=~2000) undergoing LDKT at Erasmus Medical Center (EMC) and University Medical Center Groningen (UMCG) between January 2010 and December 2020.

Methods

Retrospective data from our transplant database were used to identify patients undergoing LDKT between January 2010 and December 2020. LDKTs were categorized into male-to-male, female-to-male, male-to-female, and female-to-female groups based on donor-recipient sex combinations. The primary outcome was death-censored graft survival. The secondary outcomes included patient survival, delayed graft function (DGF), acute rejection and graft function.

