Burden and risks

N/A (no intervention involved)

Recruitment and consent

Informed consent has been waived based on the unreasonable effort due to the large size and its observational nature.

1. Introduction and rationale

The impact of donor and recipient sex combination on kidney transplant outcomes has been studied extensively, but with inconclusive results. From an immunologic perspective, the transplantation of male donor kidneys into female recipients was associated with an increased risk of graft failure and mortality due to H-Y minor histocompatibility antigens.^{1,2} Another theory, based on nephron overload and hyperfiltration, suggests that male recipients of female donor kidneys tend to experience worse outcomes due to the smaller size of female kidneys.³ Additionally, the influence of sex hormones has also been explored. Aufhauser et al.⁴ found that estrogen acts as a protective factor against ischemia-reperfusion injury (IRI), resulting in a significantly lower incidence of delayed graft function (DGF) in female recipients compared to male recipients. However, recent research by Vinson et al.⁵ demonstrates that female recipients have higher excess mortality rates and graft loss rates than males. These findings seem conflicting, and primarily focus on deceased donor kidney transplantation.

In terms of living donor kidney transplantation (LDKT), Kayler et al.⁶ analyzed a transplant database encompassing 30,258 LDKTs between 1990 and 1999. Their study revealed a significant advantage in graft survival for male recipients of male donor kidneys compared to the other combinations. Another study involving 5,716 HLA-identical sibling kidney transplantations between 1985 and 2000 demonstrated that female recipients tend to have better graft survival rates regardless of the donor's sex.³ Despite advancements in clinical practice, no such large-scale studies exploring this question have been conducted in the subsequent two decades.

2. Objective(s)

- I. To investigate the impact of different donor and recipient sex combinations on the graft survival following living donor kidney transplantation
- II. To investigate the impact of different donor and recipient sex combinations on the graft function (eGFR) following living donor kidney transplantation

3. Study type

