5.1. Research methods

Retrospective data from our transplant database were used to identify patients undergoing LDKT between January 2010 and December 2020. LDKTs were categorized into male-to-male, female-to-male, male-to-female, and female-to-female groups based on donor-recipient sex combinations. The primary outcome was death-censored graft survival. The secondary outcomes included patient survival, delayed graft function (DGF), acute rejection and graft function.

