7.2 Secondary study parameters/endpoints

The secondary outcomes included patient survival, delayed graft function (DGF), acute rejection and graft function. Graft function is defined by estimated glomerular filtration rate (eGFR) using the Chronic Kidney Disease Epidemiology Collaboration (CKD-EPI) equation.

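### eGFR, the subject of Objective II, is left to an unadjusted Kruskal-Wallis test with no time point and no measure of change, so a level difference could not be attributed to a lower start or to faster loss

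*Combined protocol and SAP*

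**What the plan says.** Section 2 lists two objectives. The second reads "To investigate the impact of different donor and recipient sex combinations on the graft function (eGFR) following living donor kidney transplantation". Section 7.2 places graft function among the secondary outcomes and says: "Graft function is defined by estimated glomerular filtration rate (eGFR) using the Chronic Kidney Disease Epidemiology Collaboration (CKD-EPI) equation". It gives no assessment time and no change or slope measure.

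Section 7.4 is the whole analysis plan. For continuous data it says "The Kruskal-Wallis test was used to compare continuous variables". Categorical data get a chi-squared test, and patient and graft survival get Kaplan-Meier curves with a log-rank test. The only regression is for the primary outcome: "Cox-regression was performed to identify the risk factors for death-censored graft failure". Section 7.4 mentions neither eGFR nor graft function, and no mixed, repeated-measures, slope or covariate-adjusted eGFR analysis appears elsewhere.

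The comparison is between four groups (section 5.1: "LDKTs were categorized into male-to-male, female-to-male, male-to-female, and female-to-female groups"). One of the theories in section 1 is that "male recipients of female donor kidneys tend to experience worse outcomes due to the smaller size of female kidneys". The Summary ties this to overload: "male recipients of smaller female kidneys have worse outcomes due to nephron overload and hyperfiltration". Sections 7.3 and 9.1 promise follow-up data in general terms and do not mention serial eGFR.

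**The concern.** The kidney-size theory allows two different patterns in eGFR. A smaller kidney may filter less from the outset and then hold steady. An overloaded kidney may start at the same level and lose function faster. The two have different implications for the patient and for donor choice, and one eGFR value per patient cannot tell them apart.

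At stake is how far Objective II can be interpreted. A reported difference in eGFR could mean either pattern. A null result could hide a true difference in decline offset by a higher starting level. The sex groups are also observational, and a Kruskal-Wallis test makes no allowance for differences between them in age or other pre-transplant factors.

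**Working it through.** **Which method reaches eGFR.** By elimination: chi-squared is for categorical variables, log-rank is for survival, and Cox is for death-censored graft failure. Only Kruskal-Wallis remains for a continuous outcome.

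**Plan's own figure.** There is none to reproduce for eGFR. Section 4.5 gives about 2000 patients with no effect size, SD or power.

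**Structure.** Let one group differ from the others by d0 at year 1 and by ds per year in slope. Its difference in level at year 5 is d0 + 4 × ds. One number cannot identify two unknowns:
- A (d0 = −4, ds = 0): −4 + 4 × 0 = −4
- B (d0 = 0, ds = −1): 0 + 4 × (−1) = −4
- C (d0 = −2, ds = −0.5): −2 + 4 × (−0.5) = −4
- D (d0 = +4, ds = −1): +4 + 4 × (−1) = 0

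This part needs no assumed SD.

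**Illustration.** From the documents: about 2000 patients, four groups, two-sided 0.05. Assumed, with no source in the documents: equal groups of 500, year-1 SD 15 (range 10 to 20), slope SD 2 per year, measurement SD 5, mean slope −1 per year, annual values in years 1 to 5, complete follow-up. There were 1000 replicates. The table gives rejection rates of a Kruskal-Wallis test applied to three different per-patient values:

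| Scenario | Year-1 level | Year-5 level | Per-patient slope |
|---|---|---|---|
| No difference | 6.4% | 5.9% | 5.0% |
| A | 98.9% | 95.5% | 6.0% |
| B | 5.0% | 95.8% | 100% |
| C | 53.1% | 96.6% | 87.1% |
| D | 98.6% | 5.5% | 100% |

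The simulated median difference at year 5 is −4.0 in each of A, B and C.

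**Hand check of A and B at year 5.** The variance is 15² + (4 × 2)² + 5² = 225 + 64 + 25 = 314. With one of four groups displaced by d, the noncentrality is (3/π) × 500 × (3/4) × d² / variance = 0.955 × 375 × 16 / 314 = 18.2 on 3 degrees of freedom. This gives a power of about 96%, in line with the simulation.

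**Range of the assumed SD** (500 replicates). With year-1 SD 10, A and B give 99.8% and 99.6% at year 5. With SD 20 they give 83.0% and 82.8%. The two stay alike throughout.

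**Smaller effects.** These runs used residual SD 6 and otherwise the same start and slope SDs; the slope test was an analysis of variance on per-patient slopes.
- Start 3 lower, same decline: year-5 level test 76%, slope test about 5%.
- Same start, 0.5 per year faster loss: 38% against 86% (41% against 86% in a second run).
- Start 3 higher, 0.5 per year faster loss (year-5 difference 3 − 4 × 0.5 = +1): 11% against 85%.

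If the slope runs from year 0 instead, the three year-5 figures become 71%, 55% and 6%. The pattern is the same.

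**The case against.** The strongest reply is that the plan has not chosen a wrong test; it has left the eGFR analysis unspecified. Section 7.4 states a general rule that may be meant mainly for baseline characteristics, and nothing says that a single late level will be compared. This stands. A reader might infer that the plan commits eGFR to such a comparison, but the text supports only that no other listed method fits and that no time point or change measure is given.

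A reader might also infer that Kruskal-Wallis can never separate the two patterns. It can if it is given per-patient slopes, as the last column of the table shows, and levels read at an early and a late time give an informal picture. The plan specifies neither. Separate tests at each visit would still give no estimate of the difference in change.

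A third tempting reading is that a fixed size difference would be a false finding. It would not. Section 7.2 defines graft function as eGFR itself, so a lasting deficit is a true effect on the stated endpoint. The 76% and 95.5% for a fixed deficit are power, not error.

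Finally, faster loss is an interpretation of hyperfiltration. The documents say only that outcomes are worse, cite other theories as well, and do not promise to test a mechanism. This stands too, but it does not remove the need to say whether Objective II concerns level, change or both.

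**Conclusion.** The point holds as a limitation of the planned eGFR analysis. For one of its two objectives, the plan offers only an unadjusted rank test with no stated time and no measure of change. Applied to level at a single time, that test gives the same answer for a fixed deficit and for faster decline, and can give none when they oppose each other. That follows from the algebra.

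The simulated rates show how large the ambiguity could be, but they rest on assumed SDs, slopes, group sizes, annual values and complete follow-up. They are not predictions for this cohort. The availability of serial eGFR values is likewise unconfirmed.

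The weight is moderate: the change is worth making before analysis, but eGFR is a secondary outcome and the analysis of death-censored graft survival does not depend on it.

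**What to change.** In section 7.4, keep Kruskal-Wallis for baseline description and add a separate paragraph for eGFR:

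- **Model.** Fit a linear mixed model to all dated follow-up eGFR values after early stabilisation, with random intercept and slope, and with sex combination, time and sex combination × time as fixed effects.
- **Adjustment.** Include pre-transplant donor and recipient covariates already collected, listed in advance. Section 7.3 names patient age and medical history but no donor variables, so the list must be checked against the database.
- **Reporting.** For each sex combination, give early eGFR level at a stated time and change per year, each with a 95% confidence interval.
- **Graft failure and death.** State how follow-up that ends in either event is treated, for example with a joint model of eGFR and the terminating event as a sensitivity analysis.

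In section 7.2, state that both early level and annual change are of interest, and the period covered.

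The cost is wording, a routine model in the R software already named, and extraction of eGFR dates with the values. Whether serial values exist at both centres should be confirmed at extraction. There are two downsides. The model assumes a time shape, which a spline can relax. Dropout may be informative if fast decliners reach graft failure or death sooner; the sensitivity analysis addresses this but does not remove it.

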4.5. Sample size calculation

To acquire enough data to make the research results robust, the estimated subject number is ~2000 patients.

5. Methods

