7.3 Other study parameters

Patient age, gender, medical history, surgical details and follow-up data.

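### The four-group log-rank comparison of patient survival cannot separate a sex-combination effect from ordinary male-female background mortality, and no within-recipient-sex contrast is specified

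*Combined protocol and SAP*

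**What the plan says.** Section 5.1 defines the comparison groups: "LDKTs were categorized into male-to-male, female-to-male, male-to-female, and female-to-female groups based on donor-recipient sex combinations". Two of the four contain only male recipients and two contain only female recipients.

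Section 7.2 lists patient survival among the secondary outcomes: "The secondary outcomes included patient survival, delayed graft function (DGF), acute rejection and graft function". It is not restricted by cause of death. Section 2 names graft survival and graft function as the objectives, and section 7.1 makes death-censored graft survival the primary outcome.

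Section 7.4 gives the only analysis of patient survival: "Kaplan-Meier curves and the log-rank test were used to compare patient and graft survival rates". The one regression in the plan has a different endpoint: "Cox-regression was performed to identify the risk factors for death-censored graft failure". The general threshold is "A two-sided p-value < 0.05 was considered statistically significant".

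Section 7.3 lists the other data held: "Patient age, gender, medical history, surgical details and follow-up data". None of these is assigned to an analysis of death. The plan has no model for death, no stratification by recipient sex, no named contrast within recipient sex and no comparison with population mortality.

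**The concern.** A four-group log-rank test has as its null hypothesis that all four survival curves are equal. Any background mortality difference between men and women makes that null false, even when donor sex does nothing and transplantation carries the same added risk in every group. A small p-value then shows that the curves differ, but not that the donor-recipient combination is the reason.

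Entering recipient sex as a covariate alongside the four-level group variable does not help, because the group already determines recipient sex.

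The problem also works in the other direction. If female recipients carried a higher transplant-related risk, their lower background mortality could offset it and the crude curves would lie together. This matters for how the result is set beside the literature: section 1 cites work reporting that "female recipients have higher excess mortality rates and graft loss rates than males", and a crude all-cause comparison is not the same quantity as excess mortality.

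At stake is the reading of one secondary result. The primary outcome does not count deaths as events, so this point does not bear on it.

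**Working it through.** **There is no plan figure to reproduce.** Section 4.5 says only that "the estimated subject number is ~2000 patients". It gives no effect size, event rate or power. The end of follow-up and the number of deaths are not stated either. All rates below are therefore assumptions, chosen to show a range.

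**Step 1: how far crude survival separates with no combination effect.** Assume constant yearly hazards, so that S(10) = exp(−10 × (background + transplant-related)), with the same transplant-related part in both sexes.

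| Scenario | Men | Women | S(10) men | S(10) women | Gap | Male:female HR |
|---|---|---|---|---|---|---|
| A | 0.010 + 0.010 = 0.0200 | 0.0065 + 0.010 = 0.0165 | 81.9% | 84.8% | 2.9 points | 0.0200/0.0165 = 1.21 |
| B | 0.006 + 0.015 = 0.0210 | 0.004 + 0.015 = 0.0190 | 81.1% | 82.7% | 1.6 points | 0.0210/0.0190 = 1.105 |

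**Step 2: how often the planned test rejects.** Assume shares of 25% male-to-male, 35% female-to-male, 22% male-to-female and 18% female-to-female, so that 60% of recipients are men. With D deaths, the 3-df log-rank statistic is approximately noncentral chi-square with noncentrality

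λ = D × Σ wᵢ(ln HRᵢ − mean)² = D × 0.6 × 0.4 × (ln HR)².

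The 5% critical value on 3 df is 7.815. For D = 300:

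- HR 1.105: λ = 300 × 0.24 × 0.0998² = 0.72, rejection about 10%.
- HR 1.21: λ = 300 × 0.24 × 0.1906² = 2.62, rejection about 24%.

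| Deaths | HR 1.105 | HR 1.20 | HR 1.21 |
|---|---|---|---|
| 200 | 8% | 16% | 17% |
| 300 | 10% | 22% | 24% |
| 400 | 11% | 29% | 32% |
| 500 | 13% | 36% | 39% |

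Equal group shares change these by no more than about 2 points. In a simulation (1,000 replicates, n = 2000, yearly hazard 0.017 in women, censoring uniform over 4 to 14 years), rejection was 5.1% at HR 1.0 and 22% at HR 1.2, in line with the formula.

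**Step 3: which death counts are plausible.** Under the same censoring assumption, the probability of an observed death at hazard h is 1 − (exp(−4h) − exp(−14h))/(10h).

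- Scenario A: 0.163 in men and 0.137 in women. With 1200 men and 800 women, that is 196 + 110 = 306 deaths.
- Scenario B: 205 + 125 = 330 deaths.

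The middle of the table is then the relevant part: rejection of roughly 10% to 25%.

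**Step 4: masking.** In scenario A, give women a further 0.0035 per year of transplant-related mortality: 0.0065 + 0.0135 = 0.0200, equal to the men. The crude curves coincide although the transplant-related hazard in women is 1.35 times that in men (0.0135/0.0100).

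**Step 5: contrasts within recipient sex.** In the same simulation, the two donor-sex log-rank statistics, one in each recipient sex, were added and tested on 2 df. Rejection was 5.1%, 4.7%, 4.0% and 4.7% at background hazard ratios of 1.0, 1.2, 1.4 and 1.6. With 1,000 replicates the Monte Carlo standard error is about √(0.05 × 0.95/1000) = 0.7 points, so these agree with 5%. This checks only that the background-mortality artefact is removed. The simulation contains no confounding by age.

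**The case against.** Four arguments on the other side have weight.

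*The plan does not say how a significant result will be interpreted.* A reader might infer that the investigators will report background mortality as an effect of the combination. The documents do not support that: section 7.4 only says that survival rates are compared. It also does not state that a single global test is the only one intended, although that is the natural reading for four groups. What stands is narrower: nothing in the plan could separate the two explanations.

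*The four curves already contain the clean comparisons.* Female-to-male beside male-to-male, and male-to-female beside female-to-female, share a recipient sex. A reader might infer that the patient-survival analysis can answer nothing. That goes too far, because the difficulty is confined to the global test and to comparisons across recipient sexes. But the within-sex comparisons are not specified, and they would be unadjusted for age.

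*Crude survival by group is a legitimate description.* Recipient sex is part of the exposure under study, and section 1 cites the excess-mortality work as one of several conflicting background findings, not as a result to replicate. The documents do not define excess mortality. This argument stands, and it is why a life-table analysis cannot be called a requirement.

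*The distortion is modest.* Under the rates assumed here, a false signal is not the most likely outcome. Far higher rejection rates appear if the background hazard ratio is set at 1.4 to 1.6, but those values lie outside the scenarios in the working and are not relied on.

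**Conclusion.** The point holds in a limited form. Patient survival is compared only by unadjusted Kaplan-Meier and log-rank across groups defined partly by recipient sex. The global test, and any contrast between male and female recipients, therefore cannot be attributed to the donor-recipient combination. With assumed male:female hazard ratios of 1.1 to 1.2 and 200 to 500 deaths, the false-signal rate is about 8% to 39% instead of 5%, and roughly 10% to 25% at the death counts those hazards imply.

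The size depends wholly on assumed hazards, group shares and follow-up. The structural point does not: it needs only some difference in background mortality by sex. It concerns a secondary outcome outside both objectives, so it is a worthwhile and cheap correction, not a threat to the main result.

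**What to change.** In section 7.4:

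1. Make the inferential analysis of patient survival the two donor-sex contrasts within recipient sex: female-to-male against male-to-male, and male-to-female against female-to-female.
2. Estimate them from a Cox model for death, adjusted for recipient age and other baseline covariates named in advance. Report hazard ratios with confidence intervals. Adjustment is needed because donor-sex groups within one recipient sex may still differ in age and other factors.
3. Keep the crude four-group Kaplan-Meier curves as description, and state that differences across recipient sexes will not be interpreted as an effect of the combination.
4. Optionally, if a statement across recipient sexes is wanted, add excess mortality against population life tables matched on age, sex and calendar year, as a sensitivity analysis.

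Items 1 to 3 are changes of wording and a model fit. Recipient age is already collected. Item 4 needs published life tables and a relative-survival routine in R.

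The cost is precision: two contrasts, each with only part of the deaths (in scenario A, about 196 in men and 110 in women), instead of one global p-value. The text should also say how the 0.05 level applies to the pair. The 4% to 5% rejection shown above is for a joint 2-df test. Two separate tests at 0.05 would give 1 − 0.95² = 9.75% for at least one rejection.

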4.3. Inclusion criteria

In order to be eligible to participate in this study, a subject must meet all of the following criteria:
Adult patients undergoing LDKT at EMC and UMCG between January 2010 and December 2020.

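### Section 7.4 plans no covariate-adjusted analysis for Objective II (eGFR) or for patient survival, DGF and acute rejection, although the sex-combination groups are observed rather than allocated

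*Combined protocol and SAP*

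**What the plan says.** Section 2 sets two objectives. The second is: "To investigate the impact of different donor and recipient sex combinations on the graft function (eGFR) following living donor kidney transplantation". Section 7.2 adds the outcomes: "The secondary outcomes included patient survival, delayed graft function (DGF), acute rejection and graft function". The groups are defined in section 5.1: "LDKTs were categorized into male-to-male, female-to-male, male-to-female, and female-to-female groups based on donor-recipient sex combinations". Section 4.3 defines the cohort: "Adult patients undergoing LDKT at EMC and UMCG between January 2010 and December 2020".

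Section 7.4 is the whole analysis plan. It gives three sets of methods:

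- Tests chosen by type of variable: "The Kruskal-Wallis test was used to compare continuous variables, and the chi-squared test was used to compare categorical variables".
- Methods for the two time-to-event outcomes: "Kaplan-Meier curves and the log-rank test were used to compare patient and graft survival rates".
- One regression model, for the primary outcome: "Cox-regression was performed to identify the risk factors for death-censored graft failure".

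The univariate screen at p < 0.1, the multivariate step and the Schoenfeld check follow the Cox sentence. Section 7.3 lists the other data collected: "Patient age, gender, medical history, surgical details and follow-up data".

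**The concern.** Both objectives are worded as the impact of sex combination, but nobody was allocated to a combination. The four groups may differ in age, in the mix of the two centres and in the year of transplant. Any of these could shift eGFR or survival without an effect of sex. A crude comparison cannot separate them.

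This matters most for eGFR, because it is one of only two stated objectives. If 7.4 is followed as written, that objective is answered by a crude test or by no named test. Patient survival, DGF and acute rejection have the same gap. They are secondary outcomes that neither objective names, so less rests on them.

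**Working it through.** **Step 1. Match each outcome to the methods in 7.4.**

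| Outcome | Unadjusted method | Adjusted model |
|---|---|---|
| Death-censored graft survival (primary, Objective I) | Kaplan-Meier, log-rank | Cox, framed as a risk-factor search with a p < 0.1 screen |
| eGFR (Objective II) | Kruskal-Wallis at most | none |
| Patient survival | Kaplan-Meier, log-rank | none |
| DGF | chi-squared at most | none |
| Acute rejection | chi-squared at most | none |

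Four of the five outcomes have no adjusted model. No other section supplies a linear, mixed or logistic model, a Cox model for death, or any matching, weighting or stratification.

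**Step 2. Allow for the two readings of the Kruskal-Wallis and chi-squared sentence.** Section 7.4 does not name eGFR, DGF or rejection. If the sentence covers all variables by type, these three get crude tests. If it covers only the baseline table, they have no stated comparison. Neither reading gives adjustment.

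**Step 3. Check what the cohort pools.** There are two centres, and transplant years 2010 to 2020 inclusive: 2020 − 2010 + 1 = 11. Neither centre nor year is named as a covariate anywhere.

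**Step 4. Check the primary model.** The Cox model serves to find risk factors, and variables enter the multivariate step by univariate p < 0.1. Nothing says that sex combination is kept if it misses that threshold. In that case the primary comparison would also rest on the log-rank test alone.

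**Step 5. Illustrate the sensitivity of a crude test.** The plan has no figure to reproduce here. Section 4.5 gives about 2000 patients, and 7.4 gives two-sided 0.05. Everything else below is assumed: four equal groups (2000/4 = 500), no true sex effect, and two groups shifted on one continuous covariate.

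- Bias in outcome SDs: b = (covariate imbalance in SDs) × (covariate-outcome correlation).
- Two of four groups shifted by b gives a sum of squared deviations of 4 × (b/2)² = b², so the noncentrality is n × b².
- Rejection rate = P(noncentral chi-square with 3 df > 7.815).
- Example: b = 0.3 × 0.3 = 0.09 and 500 × 0.09² = 4.05, so the rate is 36.3%.

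| Imbalance | Correlation 0.2 to 0.4, 500 per group | Same, 300 per group |
|---|---|---|
| 0.1 SD | 6.2% to 10.1% | 5.7% to 8.0% |
| 0.2 SD | 10.1% to 29.1% | 8.0% to 18.6% |
| 0.3 SD | 17.6% to 60.3% | 12.1% to 38.5% |

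This is a large-sample stand-in for Kruskal-Wallis. For normal data that test multiplies the noncentrality by 3/π: 4.05 × 3/π = 3.87, and the example becomes 34.7%. The table applies to eGFR only, and only on the reading where eGFR is compared by Kruskal-Wallis.

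**The case against.** Five points can be made for the plan.

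- **The multivariate sentence names no outcome, so it might cover all of them.** It directly follows the graft-failure Cox sentence, and no univariate model for another outcome exists for it to refer to. This does not stand.
- **Kruskal-Wallis and chi-squared may be meant only for the baseline table.** This is possible, and the documents do not settle it. It changes the defect for eGFR, DGF and rejection from a crude comparison to an unspecified one, and does not remove it.
- **The outcomes are secondary and no confirmatory claim is made for them.** This stands for patient survival, DGF and rejection. It is weaker for eGFR, which is an objective in its own right. For DGF and rejection no event counts are given, so adjustment may not be feasible.
- **The illustration rests on assumed inputs.** This stands in full. The documents give no eGFR SD, group sizes, imbalances or correlations, and the range runs from near nominal to severe.
- **Donor age may not be available.** Section 7.3 names only patient age, and 9.1 mentions demographics without detail. This stands, so donor age can only be a conditional covariate.

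A reader might infer that the primary outcome is properly adjusted and only the others are neglected. The documents do not support that contrast, for the reason in step 4 of the working. A reader might also take the percentages as the expected error rate of this study. They cannot be, because none of the imbalances is known.

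**Conclusion.** The point holds. As written, 7.4 answers Objective II with an unadjusted comparison at most, and compares patient survival by log-rank only. DGF and acute rejection have chi-squared at most. This follows from the text and needs no assumed figure. An adjusted primary comparison is not guaranteed either.

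How far confounding would distort the results, and in which direction, cannot be derived from the documents. The 6.2% to 60.3% range shows only how a crude test with 500 per group reacts to imbalances of 0.1 to 0.3 SD at correlations of 0.2 to 0.4. No size is claimed for patient survival, DGF or rejection. The change should be made, chiefly for eGFR. The case for DGF and rejection is weaker and depends on event counts.

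**What to change.** Keep Kruskal-Wallis and chi-squared for the baseline table, and add to 7.4:

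- **eGFR:** linear regression, or a linear mixed model if serial values are used.
- **Patient survival:** Cox regression.
- **Both models:** include sex combination and a covariate list fixed before analysis. Examples are recipient age, centre and transplant year, plus donor age if it is extracted. The sponsor may justify others from the medical history and surgical details in 7.3.
- **DGF and acute rejection:** adjusted logistic regression for DGF and an adjusted model for rejection where event counts allow. Otherwise label these comparisons descriptive.
- **Primary Cox model:** state that sex combination stays in regardless of the p < 0.1 screen.

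The cost is SAP wording, some R code and more model checks. No new patients are needed: centre and transplant year follow from the inclusion criteria, and patient age is in 7.3. The sponsor must confirm whether donor age is extracted. Event counts will limit the number of covariates. Adjustment deals only with measured and correctly modelled confounders, so the report should still state that unmeasured confounding remains.
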